1. Breast cancer mortality, as defined by the English Cancer Registry (where the initial source is the same but linkage to NBSS data more complete as uses multiple fields rather than just NHS number) checked against cause of death from the civil registrations mortality file. These sources have limited death data pre-1997, so we will also extract deaths data from NBSS to determine whether it can provide adequate quality, and if so use pre-1997. It is a binary outcome for each woman, with different lengths of follow up. Reported as cumulative incidence over all follow-up time, with focus on 10 year and 13 year to match previous systematic reviews.
2. All-cause mortality for everyone in the included cohort. This is taken from the civil registrations mortality file, which is populated by the Office of National Statistics. It is a binary outcome for each woman, with different lengths of follow up. Reported as cumulative incidence over all follow-up time, with focus on 10 year and 13 year to match breast cancer mortality.
3. Overdiagnosis. Overdiagnosis will be inferred as any difference between the study groups in total cumulative incidence of cancer (screen and symptomatic detected) after sufficient follow-up (the compensatory drop method). Therefore the outcome measured will be difference between groups in sum of breast cancers detected at screening and symptomatically. We will carefully consider length of follow-up in interpreting results relating to overdiagnosis, as insufficient follow up results in overestimation. We will publish a full protocol detailing all analysis methods and outcomes before commencing analysis to prevent selective reporting of outcomes or other analysis elements. Reported as cumulative incidence over all follow-up time, with focus on 10 year and 13 year to match breast cancer mortality.
4. Stage shift. This is defined by variables from the English Cancer Registry, including histological grade, cancer stage, and cancer size. The proposed mechanism of action of breast screening benefit is through detection of smaller earlier stage cancers. This will be measured for a combination of screen and symptomatic cancers, where differences between exposed and unexposed represents the stage shift of exposure. [In detail TNM stage (size, nodes, distant metastases), alternative nodal count to match Z11 and POSNOC trials 1/1-2/3+, DCIS vs invasive, invasive

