The NHS Cancer plan(4) extended the age range of breast screening in England from 50-64 years to 50-70 years, which was rolled out across all 80 centres between the years 2000 and 2006. The first sites to adopt the age extension were those piloting the introduction of the assistant practitioner role to assist radiographers in their work, as part of the introduction of the four tier workforce.(24) After these pilot sites, timing of roll out to other sites was dependent on funding, staffing and extra mammography equipment in place. The provision of extra equipment was lottery funded.

Within the 2000-2006 time period we will compare outcomes in women who were and were not offered two extra rounds of screening, adjusting for temporal, centre and individual level confounding. We will use the approach described by García-Albéniz et al.,(20) to emulate a weekly series of trials in which eligible women who have not yet been offered additional screening are assigned to receive or not receive screening in the coming month. Women will become eligible for the first trial on their 64th birthday*, and each woman will contribute to subsequent trials providing that she remains eligible until the day before she turns 71. We will make two sets of comparison: (a) no additional screening compared with one or more invitations to additional screening; and (b) at least two additional invitations compared with no or one additional invitation. For each weekly trial, follow-up in women in the "less screening" group will be censored at the time that receive sufficiently many invitations for inclusion in the "more screening" group. We will use inverse probability weights to adjust for

selection bias introduced by such censoring. Standard errors will be adjusted for inclusion of women in multiple weekly trials. Analyses will be by intention to screen, with women included in each group regardless of whether they attended screening. We will limit the analysis to years in which some centres had and others had not rolled out the screening age extension. We will model changes in the rate of each outcome with calendar time using cubic splines. Self-referral to screening in the years after screening will attenuate any effect, but fewer than 12% of women self-refer. **Preliminary investigation will be necessary to ascertain how the upper age limit of 64 was implemented, as it may in practice have been until a womans 65th birthday*

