Modern mammography screening in England uses two readers and arbitration of discordant assessments. Any subsequent intervention to change the recall threshold would most likely act upon each individual reader. We will use modelling approaches to evaluate the impact of test threshold on screening outcomes; we will investigate the impact of changing the process (adjusting the threshold of both readers), changing the threshold for an individual reader, the impact of one vs two readers, changing the threshold for one or both, and the pairing of readers. We will use instrumental variables to describe the recall threshold of each reader, in these proposed models. We will also model the overall effect of changing recall threshold, using a predictor for the single readers decision in the older cases where there was only one reader, and the reader combination's combined threshold in later years. This will show the relationship between the recall threshold of the system and women's outcomes.

We will investigate the mechanism of action of any effects, through intermediate outcomes. For example we expect that reduced recall threshold may increase cancer detection but change the spectrum of disease identified towards more small cancer detection (possibly of low histological grade) and also DCIS, which may in turn affect mortality and overdiagnosis. This will help our understanding of what we should aim to detect at breast screening.

A further exploratory analysis of instrumental variable approaches to recall threshold specifically for DCIS will be undertaken, as DCIS is detected predominantly through microcalcifications, and there is vigorous debate about the benefits and harms of detecting DCIS.

We will also investigate the variability between centres and readers, and its implications for screening QA targets.

Additional analyses will be conducted to investigate whether the effects of recall threshold on health outcomes vary according to age group at screening (50-60 or 61-70 years).

Sample Size Requirements

This observational data analysis does not require a formal sample size calculation. We will include every eligible case within the available cohort in analyses. However, we have included some calculations here to ensure that there are sufficient available data to enable meaningful analysis. Previous analyses have shown clustering of the proposed outcomes within centres and readers is negligible ($ICC << 0.0001$), hence the cluster of observations is

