not accounted for in these calculation; however, we will adjust for these in the analyses where appropriate.

Table 1. Sample size requirements for detecting differences within the dataset. All calculations are for 90% power at 5% significance level. There are more than 30 million screening appointments in the dataset, from more than 10 million women.

Outcome	Baseline value	Change in value	Number required in each group to detect
Intermediate outcomes			
Recall rate	3.9%	0.1%	777,920
Cancer detection rate at screening	8.4/1000	0.5/1000	679,499
Small invasive cancer detection rate at screening	3.4/1000	0.3/1000	756,401
Interval cancer over 3 years	2.9/1000	0.3/1000	640,353
False positive recalls	3.1%	0.1%	641,114
Health outcomes			
All-cause mortality	0.6050 per 100 person-years	0.6025 per 100 person years	804,400
Breast Cancer mortality	0.0443 per 100 person years	0.0433 per 100 person years	880,116
Overdiagnosis	1.3% of women invited for screening for 20 years(1)	0.1%	279,869

We will deliver three journal articles, one for each of the three questions investigated: age of eligibility; recall threshold and round length. We will submit a fourth journal article exploring the link between detection of different cancer types and outcomes, with a focus on DCIS in particular. We will also present results to the UK National Screening Committee, and inform redrafting of the English national quality assurance standards for breast screening (see work package 3).

Work Package 3: Pathway to impact (Led by [name], PHE and [name], Warwick)

In addition to journal publication there are three strands to our dissemination strategy. 1. Influencing national policy directly via the UK National Screening Committee 2. Influencing national practice through national professional guidance and communication to health professionals 3. Communication to the public

1. Influencing national policy directly via the UK National Screening Committee (UKNSC)

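### Table 1 sizes overdiagnosis as if each overdiagnosed woman could be counted (1.3% vs 1.4%), but the outcome is a difference in total breast cancer incidence, so 279,869 per group is too few for the stated 90% power

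*Protocol*

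**What the plan says.** The Sample Size Requirements section of Work Package 2 says no formal calculation is needed, but adds: "we have included some calculations here to ensure that there are sufficient available data to enable meaningful analysis". The caption of Table 1 states: "All calculations are for 90% power at 5% significance level". The row at issue gives the baseline as "1.3% of women invited for screening for 20 years(1", with a change of 0.1% and 279,869 required in each group.

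Overdiagnosis is item 3 of the primary (health) outcomes under Measuring Outcomes. Its definition begins: "Overdiagnosis will be inferred as any difference between the study groups in total cumulative incidence of cancer (screen and symptomatic detected) after sufficient follow-up". It continues: "Therefore the outcome measured will be difference between groups in sum of breast cancers detected at screening and symptomatically". On timing it says: "Reported as cumulative incidence over all follow-up time, with focus on 10 year and 13 year to match breast cancer mortality".

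Two of the three research questions list overdiagnosis among their outcomes: the age extension and the recall threshold. For the age extension, which concerns the 2000-2006 roll-out, the protocol adds: "We will limit the analysis to years in which some centres had and others had not rolled out the screening age extension".

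**The concern.** The 1.3% is an excess: the share of women whose cancer would never have come to light without screening. Under the protocol's own definition nobody can be labelled as one of these women. What is observed for each woman is whether she had any breast cancer, and overdiagnosis appears only as a difference between two groups in that proportion. Table 1 nevertheless enters the excess as if it were the observed baseline proportion, so the variance used is that of a much rarer event than the one to be analysed.

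The result is that a primary outcome looks like the easiest in the table. It has the smallest requirement of all rows; every other row needs at least 640,353 per group. A reader who relies on that figure could take a null overdiagnosis result as better powered than it was. The check of whether the data suffice has, for this outcome, been made against the wrong number.

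**Working it through.** **Inputs.** From Table 1: two-group comparison, 90% power, 5% significance (taken as two-sided, which reproduces the figure), baseline 1.3%, change 0.1 percentage points, stated n = 279,869 per group. Also from Table 1, for approximating total incidence: 8.4 per 1000 cancers detected at screening and 2.9 per 1000 interval cancers over three years.

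**Formula.** With p₂ = p₁ + d and p̄ = (p₁ + p₂)/2,

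n per group = [1.960 √(2p̄(1−p̄)) + 1.2816 √(p₁(1−p₁) + p₂(1−p₂))]² / d².

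**Step 1: reproduce the plan's figure.** With p₁ = 0.013, p₂ = 0.014, d = 0.001, the two terms are 0.31987 and 0.20915, and their sum is 0.52903. Squared and divided by 0.001², this gives 279,868.4, which rounds up to the printed 279,869. A decrease to 1.2% gives 259,400 and does not match. The row is therefore a comparison of 1.3% with 1.4%, with overdiagnosis treated as a yes/no status seen in each woman.

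**Step 2: direction of the error.** Overdiagnosed cancers are a subset of all breast cancers, so total incidence over the same period must be above the overdiagnosed share. For a fixed d and small p, n rises almost in proportion to p. Table 1 itself shows this. For the same 0.1-point change it asks for 641,114 at a 3.1% baseline (false positive recalls) and 777,920 at 3.9% (recall rate).

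**Step 3: size of the error.** The protocol states no total cumulative incidence, so what follows is an assumption. In screened women Table 1's rates add to 8.4 + 2.9 = 11.3 per 1000 per three-year round. At that pace total incidence reaches 1.3% after 3 × 13/11.3 ≈ 3.5 years. It is 0.0113 × 10/3 = 3.77% at 10 years and 0.0113 × 13/3 = 4.90% at 13 years. Halving these, to allow for a less-screened comparator, gives 1.88% and 2.45%.

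Power at the stated size is Φ{[d√n − 1.960 √(2p̄(1−p̄))] / √(p₁(1−p₁) + p₂(1−p₂))}, with d√279,869 = 0.52903. For example, at 10 years this is Φ{(0.52903 − 0.53107)/0.27096} = Φ(−0.0075) = 0.497. The detectable difference is the d at which the formula for n returns 279,869.

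| Assumed total incidence | n per group for 0.1 point, 90% power | Multiple of 279,869 | Power at 279,869 | Detectable difference at 279,869, 90% power |
|---|---|---|---|---|
| 3.77% (10 years) | 771,453 | 2.8 | 50% | 0.17 points |
| 4.90% (13 years) | 988,111 | 3.5 | 41% | 0.19 points |
| 1.88% (10 years, half rate) | 398,431 | 1.4 | 78% | 0.12 points |
| 2.45% (13 years, half rate) | 511,903 | 1.8 | 67% | 0.14 points |

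**Step 4: against the data available.** The largest of these totals is 2 × 988,111 ≈ 1.98 million women, well below the more than 10 million in the dataset. The number of women in the 2000-2006 age-extension comparison is not stated, so the same check cannot be made there.

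**The case against.** The strongest reply is that little depends on this number. The study uses every eligible record, the table is an informal feasibility check, and the row sets no recruitment target, stopping rule or analysis. More than 10 million women exceeds every corrected total above. All of this stands, and it limits the weight of the point. It does not make the printed requirement correct, and a feasibility check is useful only if it is made on the quantity to be analysed.

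A second reply is that 0.1 points is a chosen precision. Even in the least favourable case, 279,869 per group detects 0.19 points, about one seventh of the 1.3% reference. That is a fair reading, although the 1.3% refers to 20 years of invitation. It is also a reason to print the detectable difference openly.

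Third, the incidence figures are illustrative. Neither the age-extension analysis, which is by invitation and includes non-attenders, nor the threshold model starting at the final screening round amounts to continuous three-yearly screening for 13 years. The protocol's overall counts (more than 250,000 cancers in more than 35 million appointments, roughly 7.1 per 1000; both are lower bounds) with 2.9 per 1000 would give about 3.3% and 4.4%. That needs about 690,000 and 884,000 per group. So the multiple is uncertain, but every one of these scenarios lies above the stated figure.

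Finally, the 20-year basis of the 1.3% is not outside the plan, since results are reported over all follow-up and two threshold models have a 27-year horizon. The mismatch with the 10- and 13-year focus is secondary and the conclusion does not rest on it.

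**Conclusion.** The concern holds. The arithmetic of the row is right, but its baseline is wrong for the outcome the protocol defines, and 279,869 per group understates what 90% power for a 0.1-point difference requires. The direction needs only that total breast cancer incidence exceeds 1.3%. The size depends on an assumed incidence. It is about 2.8 to 3.5 times the stated number on Table 1's rates in screened women, and 1.4 to 1.8 times at half those rates, with power at 279,869 between about 41% and 78%. These are simple two-group figures; for the threshold question, where instrumental-variable models are planned, they are only indicative.

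This is a wrong requirement in a feasibility table, not evidence that the study is underpowered. For the dataset as a whole the data suffice on these assumptions. For the age-extension comparison, adequacy can be neither confirmed nor denied from the protocol.

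**What to change.** Recompute the overdiagnosis row with the total cumulative breast cancer incidence expected in the comparator group at 10 and 13 years as the baseline, and 0.1 percentage points as the between-group difference. State where that incidence comes from. Alternatively, keep a group size and restate the difference it can detect.

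Then add a sentence comparing the result with the number of women available to each analysis that reports overdiagnosis, in particular the 2000-2006 age-extension comparison.

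The cost is one table row and one sentence, with no change to design, data or analysis. The printed figure becomes less favourable.

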The possibility of misunderstanding our results will depend on the results themselves. For example, if our results suggest that the previous expansion to age 70 significantly increased the harms of breast cancer screening with few benefits there is potential for press attention and sensationalism. A potential misunderstanding would be that this means that women should not attend screening at all. To reduce these risks our strategy will emphasise maintaining control of the messaging, focusing on core messages which have been tested to minimise the chances of misunderstanding. [name] will lead the science communication, with our PPI team and radiologist co-applicants communicating what this means for patients and the NHS. We will work closely with University of Warwick and PHE communications team during the project, to synchronise messages, as we have for previous projects. The University of Warwick also has an established relationship with the Science Media centre (an independent organisation aiming to make coverage of science more balanced), and they can assist with expert reaction to controversial stories. The core messaging will be centred on improving breast screening accuracy using 30 years of NHS experience. We will work extensively with Warwick University PPI volunteers (a large and diverse group of members of the public) and with members of Independent Cancer Patients' Voice (ICPV) to reduce the possibility of misunderstanding, or unforeseen consequences of our communication with people who are not familiar with the project. In this process we will seek a broad range of perspectives from groups of different ages, sex, ethnicity, and education. We will take particular care when communicating results concerning inequalities.

Study Management

The project timings are shown in the gantt chart below:

Phase	Project Set-Up				Work Package 1: Data preparation				Work package 2: Analysis				Work Package 3: Dissemination																											
Project Month	1	2	3	4	5	6	7	8	9	10	11	12	13	14	15	16	17	18	19	20	21	22	23	24	25	26	27	28	29	30	31	32	33	34	35	36				
Calendar Month	J	F	M	A	M	J	J	A	S	O	N	D	J	F	M	A	M	J	J	A	S	O	N	D	J	F	M	A	M	J	J	A	S	O	N	D				
Approvals and set-up																																								
Milestone 1 (NHS ethics approvals)	x																																							
Milestone 2 (ODR approvals and contract signed with PHE)	x	x																																						
Milestone 3 (Subcontracts Bristol and Birmingham signed)			x																																					
Milestone 4 (Breast Research Advisory Committee approval conditions met)	x																																							
Milestone 5 (Project administrator recruited)	x	x																																						
Milestone 6 Data Transfer to Warwick			x	x																																				
Work Package 1: Data cleaning and quality																																								
Milestone 7 Single database created				x	x																																			
Milestone 8 Data cleaning complete					x	x	x	x	x	x	x	x	x	x	x	x	x	x	x	x	x	x	x	x	x	x	x	x	x	x	x	x	x	x	x					
Milestone 9 Data quality paper submitted to journal																			x																					
Milestone 10 Database transferred to Bristol and Birmingham																			x																					
Work Package 2: Analysis																																								
Milestone 11 Research Fellow employed at Bristol and Birmingham					x																																			
Milestone 12 Protocol Publication						x												x																						
Milestone 13 Analysis of screening age complete							x	x	x	x	x	x	x	x	x	x	x	x	x	x	x	x	x	x	x	x	x	x	x	x	x	x	x	x	x	x				
Milestone 14 Analysis of screening interval complete								x	x	x	x	x	x	x	x	x	x	x	x	x	x	x	x	x	x	x	x	x	x	x	x	x	x	x	x	x				
Milestone 15 Analysis of test threshold complete									x	x	x	x	x	x	x	x	x	x	x	x	x	x	x	x	x	x	x	x	x	x	x	x	x	x	x	x				
Milestone 16 Submission of 3 journal papers																										x	x	x	x	x	x	x	x	x	x	x				
Work Package 3: Dissemination																																								
Milestone 17 Policy and Practice Advisory Groups	x																								x															
Milestone 18 Website online and linked / results added		x																							x															
Milestone 19 Workshop for national champions			x																							x														
Milestone 20 Poster sent to breast screening units				x																							x													
Milestone 21 Presentation of research plan / results to all national meetings					x																							x												
Milestone 22 Presentation of results to UKNSC ARG meeting						x																							x											
Milestone 23 Recommendation of changes to breast screening quality assurance documents development and presented to group responsible for redraft							x	x	x	x	x	x	x	x	x	x	x	x	x	x	x	x	x	x	x	x	x	x	x	x	x	x	x	x	x	x				
Milestone 24 Final report complete								x	x	x	x	x	x	x	x	x	x	x	x	x	x	x	x	x	x	x	x	x	x	x	x	x	x	x	x	x				
Milestone 25 Public Dissemination complete									x	x	x	x	x	x	x	x	x	x	x	x	x	x	x	x	x	x	x	x	x	x	x	x	x	x	x	x				

There will be monthly project management meetings within each University individually. All three universities will meet at least every 3 months via online meeting space. All co-applicants and team members will meet in person annually.

[name] will lead the project and provide overall management. She will be mentored in this by [name] and [name], both of whom have extensive experience in delivering large research projects across several universities. [name] is already mentored by [name], Professor of Cancer Clinical Trials at Warwick Clinical Trials Unit.

There will be a postdoctoral research fellow at each of Warwick, Birmingham and Bristol Universities to carry out the work. Work package 1 will be undertaken primarily at Warwick, with support from Public Health England. Work package 2 analyses of age extension and screening interval will be undertaken at Bristol. Work package 2 test threshold will be undertaken primarily at Birmingham. However analysis of the overdiagnosis outcome will be led by [name] and [name] from Warwick. [name] already works part time at Birmingham and [name] holds an honorary contract there so it is an established collaboration. Work Package 3 will be led by Warwick with heavy involvement from Public Health England and all co-applicants.

There will also be a member of administrative staff employed at Warwick University responsible for coordinating the work between the three universities and Public Health England, and assisting with the administrative tasks involved in achieving all of the necessary approvals and documentation required in routine data projects.

